9.2.2 Inclusion criteria

For an eligible patient, all inclusion criteria must be answered 'yes'.

- 1. Treated with commercially available somapacitan according to local practice at the discretion of the physician.
- 2. Primary confirmed diagnosis of GHD as per local practice.
- 3. Male or female below 18 years of age at the time of signing informed consent in the GloBE-Reg.

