9.2.3 Exclusion criterion

For an eligible patient, the following exclusion criterion must be answered 'no'.

1. Patients with active malignancy or in treatment for active pre-existing malignancy.

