9.2.4 Rationale for selection criteria

The study population comprises all patients eligible according to the inclusion and exclusion criteria for this registry-based study as well as the inclusion and exclusion criteria defined for inclusion in the GloBE-Reg. The eligibility criteria have been kept to a minimum to ensure that the study population will represent the broader real-world population of paediatric patients with GHD treated with somapacitan.

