9.7 Data analysis

9.7.1 Definition of analysis sets

The safety analysis will be based on the SAS. The SAS will consist of all patients exposed to somapacitan during study period.

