9.7.2.1 Analysis of primary endpoint

The primary endpoint is the number of ADRs from baseline to EOS. EOS will differ from patient to patient.

ADRs during the study period will be summarised by MedDRA SOC and PT. This summary is displayed with number and proportion of patients with at least one event, number of events, and event rate (events per 100 patient-years of exposure).

The combined data from NordiNet® IOS and ANSWER will be used as an external comparator for the occurrence of ADRs. The aggregated data from isolated GHD patients from the NordiNET/ANSWER study will be used for comparison of both baseline characteristics and ADR incidence rates. No statistical comparison is planned due to limitations in the observational nature of the data collection.

The correlation between ADR incidence and duration of somapacitan treatment will be analysed with Spearman rank-order correlation.

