9.7.2.2 Analysis of secondary endpoints

Binary secondary endpoints:

The binary secondary endpoints include:

- Incident neoplasm
- Incident T2DM

Incidence rates will be calculated for both endpoints and compared to aggregated data of incident neoplasms from the combined NordiNET/ANSWER study⁶ and incident T2DM from the GeNeSIS study.⁹ From both studies, the incidence rates for isolated GHD will be used for comparison. The SIR with a 95% confidence interval will be used as an additional estimate for neoplasms and new-onset T2DM.

 Protocol
 Date:
 17 July 2024
 Novo Nordisk

 Study ID: NN8640-4787
 Version:
 3.0
 3.0

 UTN: U1111-1294-5941
 Status:
 Final

Page:

25 of 48

Count-data secondary endpoints:

The analyses of the following secondary endpoints (counted from the baseline (week 0) to the EOS^a) will be done in the same way as the analysis of the primary endpoint:

• Number of AEs

EU PAS No.: Pending

- Number of SAEs
- Number of serious ADRs
- Number of medication errors

Continuous secondary endpoints

For the following secondary endpoints (clinical parameters), the change will be estimated by length of follow up and treatment duration.

- Height velocity
- Change in height velocity SDS
- Change in height SDS
- Change in IGF-I SDS
- Change in bone age

Patients reaching near adult height will be evaluated at EOS only for those who are expected to reach near adult height during the study. Change in height SDS in subjects reaching near adult height will be calculated from baseline (week 0) to EOS.

Note: Near adult height can be defined as height velocity <2 cm/year over the last 9 months and chronological age >16 years (males) or >15 years (females) or bone age >16 years (males) and >15 years (females).

IGF-I SDS will be used to evaluate treatment adherence assuming an increase in IGF-I SDS represents a response to GH treatment.

To deal with patients switching medication in-study and on-treatment analyses will be performed as defined below. The analyses will be repeated separately for GH treatment naïve and non-naïve patients previously receiving other GH treatment as data allows.

In-study

The observation period represents the time frame during which patients are considered to be part of the study, regardless of their adherence to somapacitan treatment. The in-study period starts at the time of informed consent and ends at the date of whichever comes first:

- EOS visit (last visit within the study duration)

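### The external benchmarks are isolated-GHD rates, but the somapacitan side is every exposed child with any confirmed GHD, so case mix alone can move the comparison, chiefly for neoplasms and T2DM

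*Protocol*

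**What the plan says.** **Comparator side.** For ADRs, Section 9.7.2.1 says: "The aggregated data from isolated GHD patients from the NordiNET/ANSWER study will be used for comparison of both baseline characteristics and ADR incidence rates". For incident neoplasm (NordiNet IOS/ANSWER) and incident T2DM (GeNeSIS), Section 9.7.2.2 says: "From both studies, the incidence rates for isolated GHD will be used for comparison". Sections 4.7 and 4.10 repeat the restriction.

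**Somapacitan side.** The diagnostic criterion in Section 9.2.2 is "Primary confirmed diagnosis of GHD as per local practice". The only exclusion, in Section 9.2.3, is "Patients with active malignancy or in treatment for active pre-existing malignancy". Section 9.2.4 explains that this breadth is deliberate: "The eligibility criteria have been kept to a minimum to ensure that the study population will represent the broader real-world population". Section 9.7.1 adds: "The SAS will consist of all patients exposed to somapacitan during study period".

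**Type of comparison.** For ADRs, Section 9.7.2.1 rules out a statistical comparison. For neoplasms and T2DM, incidence rates are compared with the published ones, and "The SIR with a 95% confidence interval will be used as an additional estimate for neoplasms and new-onset T2DM". That sentence does not name the reference population for the SIR.

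**Variables.** Section 9.3.3 lists, among others, history of neoplasms and history of T2DM, but not GHD type or aetiology. The analyses by subgroup in Section 9.7.2.2 cover prior GH treatment (naïve or not), sex, age, dose, country or region, and Tanner stage. None is by GHD type.

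**The concern.** One side is restricted by GHD type and the other is not. On the text as written, children with non-isolated GHD, and children with a past malignancy no longer active or under treatment, may enter the somapacitan rates. The benchmark is confined to isolated GHD.

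The shift to isolated GHD is also unexplained. Section 8.2 sets the objective as comparison with paediatric GHD patients on daily somatropin. Section 7 introduces the comparators through their GHD totals (around 22,000 and 7,523). The 2% ADR incidence used for planning in Section 9.5 is for paediatric GHD patients, not stated to be isolated GHD.

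Neoplasms and T2DM are a special focus of the primary objective, and Section 7 relies on the historical comparison for conclusions on long-term safety. If event rates differ by GHD type, a difference from the benchmark cannot be attributed to the drug.

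**Working it through.** **1. The plan's own figure.** Table 9-4 uses the Wilson interval, with centre (p + z²/2n)/(1 + z²/n) and half-width [z/(1 + z²/n)]·√(p(1-p)/n + z²/4n²). With p = 0.02, n = 400 and z = 1.96, the interval is 1.02% to 3.90%. The table gives 1.02 to 3.89, a rounding difference. The other rows agree to within 0.01 point. The sample-size table is sound for what it states; the issue here is which population the rates describe.

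**2. The two sides.**

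| Item | Somapacitan | External benchmark |
|---|---|---|
| GHD type | Any confirmed GHD (9.2.2) | Isolated GHD (9.7.2.1, 9.7.2.2) |
| Malignancy | Only active, or under treatment, excluded (9.2.3) | Not stated in the protocol |
| Analysis set | All exposed (9.7.1) | Published aggregate |
| GHD type as variable | Not listed (9.3.3, 9.7.2.2) | Fixed by the restriction |

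No section restricts the somapacitan side to match.

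**3. Effect of case mix with no drug effect.** Let f be the non-isolated share of the somapacitan cohort and k the event rate in non-isolated relative to isolated GHD. Then

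apparent ratio = (1-f) + f·k.

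The protocol gives neither f nor k. All values below are assumptions.

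| f | k=0.5 | k=1 | k=2 | k=5 |
|---|---|---|---|---|
| 10% | 0.95 | 1.0 | 1.1 | 1.4 |
| 20% | 0.90 | 1.0 | 1.2 | 1.8 |
| 30% | 0.85 | 1.0 | 1.3 | 2.2 |

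Example: f = 20%, k = 5 gives 0.8 + 0.2×5 = 1.8. A ratio of 2 from case mix alone needs k = 1 + 1/f, which is 11, 6 and 4.3 for f = 10%, 20% and 30%.

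**4. ADR illustration.** Take 2% as the isolated-GHD risk (an assumption, see above), with f = 20% and k = 3. The cohort risk is 2%×(0.8 + 0.2×3) = 2.8%. At that observed value and n = 400 the Wilson interval is 1.58% to 4.92%. It no longer excludes the doubling to 4% that Section 9.5 is sized to rule out, although the drug has no effect.

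**5. SIR illustration, only if the SIR were indexed to isolated-GHD rates.** With 2 expected events (assumed), the chance that the exact 95% lower limit exceeds 1 is 2% at a ratio of 1 and 16% at a ratio of 1.8.

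**The case against.** **The protocol may not be as broad as it looks.** Inclusion of non-isolated GHD is read from the lack of a restriction. Section 9.2.2 uses the word primary, and Section 9.2.4 says that the registry's own entry criteria also apply; these are not shown. This stands as a caveat. If isolated GHD was meant, the criterion should say so, so the text needs correcting either way.

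**The mismatch could be repaired later.** A reader might infer that the listed data make it irreparable. The protocol does not support that. Section 9.3.3 lists characteristics that overlap with the comparator studies, and Tanner stage is a planned subgroup although it does not appear in Section 9.3. The list is not exhaustive, so GHD type may be available in the registry, and prior neoplasm is already listed. But no planned analysis uses GHD type for the comparison, and the protocol itself fixes the comparator side.

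**No rate ratio is planned.** Correct. ADRs are compared descriptively, and the SIR reference is unnamed. The SIR precedent described in Sections 7 and 9.1.1 used a US youth diabetes study, not isolated-GHD rates. The mixture formula therefore describes the side-by-side comparison of rates and may not apply to the SIR.

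**The size is assumed.** Also correct. A reader might infer a false signal of a particular size, or a masked one. The protocol supports neither: masking by this route needs k below 1, and no figure shows k on either side of 1.

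**It is acknowledged.** Baseline characteristics will be compared with the isolated-GHD data. Section 9.9 names medical history and previous GH treatment as potential confounders and promises a discussion of comparability. It does not name GHD type, and a discussion does not align the populations.

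**Conclusion.** The mismatch is in the text and should be fixed. As written, rates from an all-GHD cohort are set beside isolated-GHD rates, and case mix can separate them without any drug effect. The consequence is sharper for neoplasms and T2DM than for ADRs.

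Its size and direction are unknown. Under assumed inputs the apparent ratio is 1.1 (f = 10%, k = 2) to 1.8 (f = 20%, k = 5), it is below 1 if k is below 1, and there is no bias at k = 1. The conclusion that the populations differ rests on reading Section 9.2.2 as admitting any confirmed GHD.

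A reader might infer that the study's main safety result is compromised. It is not: the summary of ADRs by SOC and PT does not depend on the benchmark, and the external comparison is a secondary objective.

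**What to change.** 1. In Sections 4.7, 4.10, 9.7.2.1 and 9.7.2.2, make each comparison with isolated-GHD rates, including the baseline table, in the isolated-GHD subset of the somapacitan cohort. Report the full cohort separately, without that benchmark.
2. List GHD type or aetiology in Section 9.3.3 as an extracted variable.
3. Exclude patients with a history of neoplasm from the neoplasm comparison only if the comparator rates exclude them too. Otherwise show the exclusion as a sensitivity analysis: applied to one side only, it could create a new mismatch that lowers the somapacitan rate.
4. State that patients with prevalent T2DM contribute no person-time to the incident T2DM rate. The endpoint is already incident T2DM; this settles the denominator.
5. If the diagnosis criterion was meant as isolated GHD, say so in Sections 4.6.1 and 9.2.2.

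**Cost.** One listed variable and some analysis wording. The comparison will have fewer patients and wider intervals, while the full-cohort results remain. Data collection runs to Q4 2034, and the variable is best secured early.

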8.2 Secondary objectives

- To investigate safety and clinical parameters of somapacitan treatment in paediatric patients with GHD in the setting of routine clinical practice.
- To compare the occurrence of AEs, SAEs, serious ADRs including neoplasms and T2DM in patients treated with somapacitan with historical data from literature (NordiNet® IOS, ANSWER studies and GeNeSIS registry) paediatric GHD patients treated with daily somatropin.

 Protocol
 Date:
 17 July 2024
 Novo Nordisk

 Study ID: NN8640-4787
 Version:
 3.0
 Status:
 Final

Page:

18 of 48

[figure not shown]
9 Research methods

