9.5 Study sample size

The sample size calculations are performed for the primary endpoint (number of ADRs) and based on previous experience from the NordiNet[®] IOS⁶ where 2% of the paediatric patients with GHD experienced an ADR.

Table 9-4 shows the 95% confidence interval for an incidence of 2%, derived using the Wilson-score method.

Table 9-4 Sample size table (Wilson-score method)

Sample size	95% CI
100	(0.55, 7.00)
200	(0.78, 5.02)
300	(0.92, 4.29)
400	(1.02, 3.89)
500	(1.09, 3.64)

Based on the table above, a sample size of at least 400 patients (inclusive of both naïve and non-naïve paediatric patients) would be required to rule out the doubling of the incidence for ADRs. Therefore, the study is planned for the sample size of 400 patients.

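### N=400 is justified by a confidence interval that would exclude a doubling of ADR incidence, but the planned primary analysis is descriptive and disclaims any statistical comparison

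*Protocol*

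**What the plan says.** **Sizing (Protocol 9.5).** "The sample size calculations are performed for the primary endpoint (number of ADRs"), with a reference taken from NordiNet IOS, "where 2% of the paediatric patients with GHD experienced an ADR". The supporting tabulation (Table 9-4) covers sample sizes from 100 to 500; it "shows the 95% confidence interval for an incidence of 2%, derived using the Wilson-score method". From the table the section concludes that at least 400 patients "would be required to rule out the doubling of the incidence for ADRs", and closes: "Therefore, the study is planned for the sample size of 400 patients".

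**Primary analysis (Protocol 9.7.2.1).** ADRs are tabulated by MedDRA class and term. The table shows how many patients had one, as a number and a proportion, how many events occurred, and the rate per 100 patient-years of exposure. Aggregated isolated-GHD data from NordiNet IOS and ANSWER combined serve as the external comparator for baseline characteristics and ADR incidence rates. The next sentence reads: "No statistical comparison is planned due to limitations in the observational nature of the data collection". The only other analysis is a Spearman correlation of ADR incidence with treatment duration.

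**Secondary analysis (Protocol 9.7.2.2).** "The SIR with a 95% confidence interval will be used as an additional estimate for neoplasms and new-onset T2DM". The count-type secondary endpoints follow the method of the primary endpoint, so the disclaimer carries over to them.

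**The concern.** Ruling out a doubling is a statement about a parameter relative to a reference value. It needs no hypothesis test, but it does need an interval and a threshold to read it against. Section 9.5 has both: the Wilson 95% interval, and 4% as twice 2%. The section that describes the primary analysis has neither, and it adds a sentence that disclaims the comparison.

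At stake is whether this post-authorisation safety study answers the question used to justify its size. Under 9.7.2.1 the report would set an observed ADR figure beside a published one, with no planned statement on whether a doubling has been excluded. An SAP that elaborates the protocol faithfully would inherit the disclaimer, so the conflict should be settled in the protocol.

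**Working it through.** **Inputs.** From 9.5: reference proportion p = 0.02, two-sided 95% level (z = 1.96), Wilson score method, planned n = 400. The threshold is 2 × 2% = 4%; it is implied by the doubling wording and not written as a number.

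**Step 1: reproduce Table 9-4.** The Wilson interval without continuity correction is

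[p + z²/(2n) ± z·√(p(1−p)/n + z²/(4n²))] / (1 + z²/n).

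For n = 400 and p = 0.02:
- centre = (0.02 + 3.8416/800) / (1 + 3.8416/400) = 0.024802/1.009604 = 0.02457
- half-width = 1.96 × √(0.0196/400 + 3.8416/640000) / 1.009604 = 1.96 × 0.007416/1.009604 = 0.01440
- interval = 1.02% to 3.90%

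| n | Table 9-4 (%) | Recomputed (%) |
|---|---|---|
| 100 | 0.55, 7.00 | 0.55, 7.00 |
| 200 | 0.78, 5.02 | 0.78, 5.03 |
| 300 | 0.92, 4.29 | 0.92, 4.29 |
| 400 | 1.02, 3.89 | 1.02, 3.90 |
| 500 | 1.09, 3.64 | 1.09, 3.64 |

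The table is right to within 0.01; two upper limits look truncated rather than rounded. Of the tabulated sizes, 400 is the smallest with an upper limit below 4%. Over all n at exactly 2%, the smallest is 369. The sizing arithmetic is sound, and the threshold is what selects 400.

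**Step 2: look for that threshold in the analysis.** Section 9.7.2.1 contains no interval, no 4% and no rule for concluding that a doubling is excluded. The abstract (4.10) does not supply them either. The Spearman correlation addresses treatment duration, not the comparator. The only planned 95% interval is for the standardised incidence ratio of neoplasms and T2DM (4.10 and 9.7.2.2).

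**Step 3: what the conclusion would need at n = 400.**

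| Patients with an ADR | Proportion | Wilson 95% interval | Upper limit below 4%? |
|---|---|---|---|
| 7 | 1.75% | 0.85% to 3.57% | yes |
| 8 | 2.00% | 1.02% to 3.90% | yes |
| 9 | 2.25% | 1.19% to 4.22% | no |
| 10 | 2.50% | 1.36% to 4.54% | no |

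The cut-off is 8 patients, which is also the expected number at 2% (0.02 × 400 = 8). One further patient changes the conclusion, and a bare proportion does not show this.

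**Step 4: how often it would be reached.** With X the number of patients with an ADR, binomial with n = 400:
- if the true incidence is 2%, P(X ≤ 8) = Σₖ₌₀⁸ C(400,k)·0.02ᵏ·0.98⁴⁰⁰⁻ᵏ = 0.593
- if the true incidence is 4%, P(X ≤ 8) = 0.020, the chance of wrongly excluding a doubling

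For scale, the first probability is 0.698 at n = 500 (cut-off 11) and 0.913 at n = 800 (cut-off 21).

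**Step 5: check that the two sections use the same reference.** They do not. Section 9.5 takes a proportion of GHD patients from NordiNet IOS alone. Section 9.7.2.1 uses incidence rates in isolated GHD from NordiNet IOS and ANSWER combined. A reporting rule has to say which figure is doubled.

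**The case against.** The best defence has four parts.

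- **The interval belongs in the SAP.** Section 4.10 promises an SAP with the detailed analyses, and 9.7.2.1 does not forbid intervals. This stands: a missing interval alone would not be a finding. A reader might infer that the doubling question can never be answered. The document does not support that, because the SAP is not shown and a Wilson interval can be computed from the reported number of patients. What the SAP cannot quietly settle is the conflict between an express disclaimer and an express sizing rationale.
- **The disclaimer may mean only that no between-cohort test is done.** That is a fair reading, since it follows the sentence on the external data. A single-arm interval read against 4% would be compatible with it. The protocol does not say so, however, and the rewording below would.
- **Section 9.5 gives a reason for N, not a reporting rule.** This is correct, and 9.5 should not be read as promising a stated conclusion. But its reason is exclusion of a doubling, not precision alone.
- **The comparison objective is not broken.** A reader might see a contradiction with 8.2, "To compare the occurrence of AEs, SAEs, serious ADRs including neoplasms and T2DM in patients treated with somapacitan with historical data from literature". That goes too far: 8.2 does not name all ADRs, which is the endpoint sized, and the descriptive comparison in 9.7.2.1 is still a comparison. Nor does the interval for neoplasms and T2DM oblige one for ADRs, which depend on physicians' causality judgements (9.9). It shows only that observational data are not in themselves a bar to interval estimation.

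It is also tempting to turn the 8 expected patients into an event rate over total follow-up. The document does not support this: a patient may have several ADRs, and 9.1 continues follow-up after somapacitan is stopped, so follow-up time is not exposure time.

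**Conclusion.** The inconsistency is real and concerns the primary endpoint. The protocol chooses 400 patients to exclude a 4% ADR incidence, then describes a primary analysis that does not draw that conclusion and disclaims statistical comparison. Nothing elsewhere in the protocol reconciles the two. The defect is the missing link between sizing and analysis; Table 9-4 itself is correct.

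The cut-off is 8 of 400 patients, reached with a probability of about 59% at a true 2%. These figures assume exactly 400 patients, independent patients, and the 2% reference taken as a fixed value that applies to comparable follow-up.

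**What to change.** In 9.7.2.1:

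1. Report the two-sided Wilson 95% interval for the proportion of patients with at least one ADR, and read its upper limit against the 4% implied by 9.5.
2. Name the comparator figure being doubled and reconcile the NordiNet IOS GHD proportion in 9.5 with the isolated-GHD rates from the combined studies in 9.7.2.1.
3. Give a 95% interval for the ADR rate. A ratio to the external rate is optional; the protocol does not state the comparator rate it would need.
4. Replace the disclaimer with wording such as: *no formal hypothesis test is planned; interval estimates are interpreted in light of the limitations in 9.9*.

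Alternatively, withdraw the doubling rationale from 9.5 and justify 400 patients by the width of the interval only (about 1.0% to 3.9% at an observed 2%).

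The cost is protocol and SAP wording plus a few table columns; no new data are needed and N does not change. If the first route is taken, the protocol should state its downside: at 400 patients the upper limit falls below 4% only with 8 or fewer affected patients, about a 59% chance at a true 2%. Failure to exclude a doubling would therefore not by itself indicate an excess.

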9.1 Study design

EU PAS No.: Pending

This is a non-interventional, multi-national, single-treatment arm, observational, registry-based study to investigate the long-term safety and clinical parameters of somapacitan in paediatric patients with GHD under routine clinical practice conditions. The study design is shown schematically in Figure 9-1.

Figure 9-1 Schematic diagram of the study design

Abbreviations: GHD = growth hormone deficiency, FPFV = first patient first visit, LPFV = last patient first visit, and LPLV = last patient last visit.

The study population will consist of at least 400 paediatric GHD patients from the GloBE-Reg registry treated with once-weekly somapacitan and fulfilling the eligibility criteria of the present study (see Sections 9.2.2 and 9.2.3). The total duration of the study is planned for 10 years consisting of a 5-year recruitment period in the registry followed by a follow-up period of at least 5 years. Individual patients will be followed up from inclusion into GloBE-Reg until last routine visit within the full study duration, i.e. individual follow-up time is expected to be above 5 years. Patient data are planned to be collected beyond the age of 18 years and irrespective of discontinuation of somapacitan. The main purpose of this study is to observe patients for long-term safety. The planned study duration is from Q4 2024 until Q4 2034.

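### The Spearman correlation of ADR incidence with treatment duration is not centred on zero when the ADR rate is constant, so neither its sign nor its size shows whether risk changes with longer treatment

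*Protocol*

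**What the plan says.** Protocol section 9.7.2.1 defines the outcome as a cumulative count over a patient-specific period: "The primary endpoint is the number of ADRs from baseline to EOS. EOS will differ from patient to patient". It plans a descriptive summary by SOC and PT with patients affected, "number of events, and event rate (events per 100 patient-years of exposure"), and then adds: "The correlation between ADR incidence and duration of somapacitan treatment will be analysed with Spearman rank-order correlation".

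The section does not say whether incidence here means a count, ever/never, an individual rate or a rate per duration interval. It names no unit of analysis and makes no provision for patients who stop because of an ADR.

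Section 9.7.2.2 says that AEs, SAEs, serious ADRs and medication errors "will be done in the same way as the analysis of the primary endpoint".

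On follow-up, section 9.1 states that "individual follow-up time is expected to be above 5 years", within a 10-year study that recruits for 5 years. It also says that data are collected irrespective of discontinuation, so treatment can be shorter than follow-up. Section 9.7.2.2 ends the on-treatment period at treatment stop, if that comes first.

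**The concern.** Treatment duration is the window in which an on-treatment ADR can occur. With a constant ADR rate, patients treated for longer have more ADRs simply because they had more time, and a patient-level rank correlation turns this into a positive coefficient. Dividing each patient's count by duration does not cure this when ADRs are rare. Almost all patients are tied at zero, and the ranks mainly separate those with an ADR from those without. If ADRs lead to stopping, those patients have short durations because of the ADR, and the sign can reverse.

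This matters because section 7 gives long-term safety as the missing information that the study is meant to supply: the submission held no data beyond 52 weeks of exposure. The correlation is the only stated analysis relating ADR risk to length of treatment. The events per 100 patient-years summary is one overall rate and cannot show change over time, and the listed subgroups do not include treatment duration.

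**Working it through.** **Inputs from the protocol.** Section 9.5 gives the ADR proportion ("where 2% of the paediatric patients with GHD experienced an ADR") and the number of patients ("Therefore, the study is planned for the sample size of 400 patients"). Five-year recruitment within ten years (section 9.1) implies follow-up of roughly 5-10 years.

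**Assumptions not in the protocol.** Treatment duration is uniform on 5-10 years (A) or 0.5-10 years (B). The share of ADR patients who stop at the ADR is 0, one half or all. The ADR rate is constant, so the true duration effect is nil.

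**The plan's own figure.** Section 9.5 "shows the 95% confidence interval for an incidence of 2%, derived using the Wilson-score method". Recomputing at n=400 gives (1.02, 3.90) against the printed (1.02, 3.89). The other rows of Table 9-4 also agree to within 0.01. The sample-size table is sound and is not affected by this point.

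**Approximate formula.** For a yes/no ADR, Spearman's rho is the ordinary correlation between the ADR indicator and the rank of duration. Scale the ranks to 0-1, with mean 1/2 and SD 1/√12. Let p be the proportion with an ADR and m the mean scaled rank of duration among ADR patients. For small p,

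rho ≈ √12 × (m − 1/2) × √(p/(1−p)).

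At p = 0.02 the multiplier is 3.464 × 0.1429 = 0.495.

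For durations from a to a+w, with mean a + w/2:

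- No ADR-driven stopping: m = (a/2 + w/3)/(a + w/2). A: (2.5 + 1.667)/7.5 = 0.556. B: (0.25 + 3.167)/5.25 = 0.651.
- Every ADR stops treatment: m = (w/6)/(a + w/2). A: 0.833/7.5 = 0.111. B: 1.583/5.25 = 0.302.
- Half stop: the average of the two. A: 0.333. B: 0.476.

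**Results at p = 0.02, n = 400, no true duration effect.** Simulated values are rounded over runs of 1,000 to 3,000 replicates.

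| Durations | ADR patients stopping | rho by formula | rho simulated | p<0.05 simulated |
|---|---|---|---|---|
| A, 5-10 y | none | 0.495 × 0.056 = 0.03 | 0.03 | about 8% |
| A | half | 0.495 × (−0.167) = −0.08 | −0.08 | about 40% |
| A | all | 0.495 × (−0.389) = −0.19 | −0.19 | about 95% |
| B, 0.5-10 y | none | 0.495 × 0.151 = 0.07 | 0.07 | about 30% |
| B | half | 0.495 × (−0.024) = −0.01 | −0.01 | about 6% |
| B | all | 0.495 × (−0.198) = −0.10 | −0.10 | about 48% |

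The formula and the simulation agree. In B with half stopping the two biases nearly cancel, so a rho near zero is no evidence of an unchanged risk.

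**More frequent events.** With 10% of patients having an ADR and no ADR-driven stopping, rho is 0.06 (A) and 0.17 (B), with p<0.05 in 22% and 94%. Individual rates instead of counts give 0.04 and 0.15, with 14% and 86%. For AEs at an assumed 30 per 100 patient-years and durations B, the count-based rho averages 0.57, with p<0.05 in every simulated study.

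**Person-time alternative.** First ADRs and time at risk were allocated to years since treatment start, and a score test for trend in the rate was applied. It rejected in 4.2-5.5% of studies in all 12 scenarios run: durations A, or A with 10% per year unrelated stopping; 2%, 10% or 30% with an ADR; none or all stopping at the ADR. Nominal is 5%.

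**The case against.** The strongest reply has four parts.

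*Size.* In the scenario nearest the protocol's follow-up statement (5-10 years, 2% with an ADR, no ADR-driven stopping) the bias is small: rho about 0.03, with p<0.05 in about 8%. The larger figures need a wider duration spread, more events or ADR-driven stopping, none of which the protocol quantifies. Stopping after every ADR is an extreme case. This stands, and is why a range is given. However, half of ADR patients stopping is enough to give about −0.08 and 40% at 5-10 years.

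*Status.* A reader might infer that the study would declare a duration effect where none exists. The protocol does not support that. It states no hypothesis, alpha or decision rule for this correlation, and the coefficient stands beside counts, proportions and rates that are unaffected. The p<0.05 frequencies measure how far the coefficient is displaced; they are not the error rate of a planned test.

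*Definition.* Section 4.10 leaves detail to a SAP that is not shown, and incidence is undefined. That is fair for the definition, but not for the method, which the protocol fixes. With rare ADRs, none of the patient-level versions (count, ever/never, individual rate) is generally centred on zero. Individual rates largely work only for frequent AEs with durations of 5-10 years (p<0.05 in about 7%). A Spearman correlation across yearly interval rates avoids the opportunity mechanism, but was also off-centre with sparse events (mean rho −0.05 to −0.31).

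*Remedy.* A categorical regression over time intervals fails when ADRs are rare. At 2% of 400, about 8 patients have an ADR. With intervals 0-1, >1-2, >2-5 and >5 years and durations A, the expected numbers are 8 × (1, 1, 3, 2.5)/7.5 = 1.07, 1.07, 3.20 and 2.67. The chance that at least one interval is empty is 1 − (1−e^−1.07)² × (1−e^−3.20) × (1−e^−2.67), about 62%; under B it is about 52%. This stands, and it limits the fix.

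**Conclusion.** The point holds as a fault in a stated method. The patient-level correlation reflects opportunity time and discontinuation as well as risk, and the two pull in opposite directions. At n=400, 2% with an ADR and no true duration effect, rho runs from about +0.07 to about −0.19 across the assumed scenarios, with p<0.05 in about 6% to 95%. The mildest positive case is about 0.03 and 8%. The bias is usually larger for more frequent events, which matters because AEs are analysed in the same way.

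These sizes rest on assumed duration spreads and stopping shares. The direction of each bias does not depend on the exact values. The consequence is a misleading estimate, in either direction or falsely reassuring, on the question the study was set up to answer. The sample size, the primary endpoint and the overall rates per 100 patient-years are untouched.

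**What to change.** Replace the Spearman sentence in section 9.7.2.1 with text such as: *ADR rates will be estimated by time since start of somapacitan (for example 0-1, >1-2, >2-5 and >5 years), counting only events and person-time at risk within each interval, with exact Poisson 95% confidence intervals. Where event numbers allow, a one-degree-of-freedom test for trend in the first-event rate over time on treatment will be reported, with person-time as denominator.*

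Apply the same to SAEs, serious ADRs and medication errors, and to AEs. Keep Poisson or negative binomial regression with a log person-time offset for frequent events such as AEs, since interval contrasts for rare events will often not be estimable.

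The cost is a short text change and slightly more programming. Intervals will be wide when events are few, which shows honestly what the data can say. Treatment start, treatment stop and event dates suffice, so no new data are needed.
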